9.3 Analysis Sets

For the purposes of analysis, the following analysis sets are defined:

Participant Analysis Set	Description	
Randomized	Participants who were randomly assigned to either the nirsevimab group or the control group	
Safety Analysis Set (SafAS)	Participants who received nirsevimab in the study and all randomized participants if randomized to the control group and who did not receive nirsevimab inadvertently. All participants will have their safety analyzed according to the study intervention they actually received.	
Per-Protocol Analysis Set (PPAS)	All randomized participants who did not have at least one of the following protocol deviations:	
	- Participant did not meet all protocol-specified inclusion criteria or met at least one of the protocol-specified exclusion criteria	
	- Participant did not receive nirsevimab or the correct dose of nirsevimab if randomized to nirsevimab	
	- Participant received nirsevimab if randomized to no intervention	
	- Administration of nirsevimab was not done as per-protocol	
	- Participant did not have at least one contact for efficacy follow-up after dosing/randomization	
	- Any other protocol deviations identified during the study conduct as relevant to the exclusion from the PPAS	
	All participants will have their efficacy endpoints analyzed according to the group they were randomized to.	

9.4 Statistical Analyses

The statistical analysis plan (SAP) will include a more technical and detailed description of the statistical analyses described in this section. This section is a summary of the planned statistical analyses of the most important endpoints including primary and key secondary endpoints.

9.4.1 General Considerations

There will be 3 planned main analyses for this study: the Primary Analysis, the First Year Analysis, and the Second Year Analysis. The Primary Analysis will be conducted when at least 61 events of RSV LRTI hospitalization in all 3 countries combined are observed, but no later than 30 April 2023. All available data collected up to the data cut-off date will be analyzed at the time of the Primary Analysis. The First Year Analysis will be conducted when all participants have completed the scheduled 12-month safety follow up. It will include all data and planned analyses. The Second Year Analysis will be conducted when all UK reconsented participants have completed the scheduled 24-month safety follow-up. It will include all data and planned analyses.

The efficacy analyses performed in the Primary Analysis will serve the purpose of evaluating the efficacy of nirsevimab in the study population. LRTI hospitalization will also be collected after the end of the RSV season and the efficacy will be calculated but only for descriptive purposes at the time of the First Year Analysis without the intention of a confirmatory conclusion. LRTI hospitalizations and wheezing episodes will also be collected at 24 months follow-up and at 12 and 24 months follow-up, respectively, in UK reconsented participants but only for descriptive purposes at the time of the Second Year Analysis (without the intention of a confirmatory conclusion for LRTI hospitalizations). Therefore, no multiplicity adjustment is needed for the 3 main analyses.

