A follow-up phone call will be made to the parents or LARs of the participant by the site personnel or designee at D366 (end of the study for France, Germany, and non-reconsented UK participants) to collect any safety event that may have occurred in the 6-month period since the last electronic contact.

Two additional follow-up phone calls – at D546 and D731 post-dosing/randomization (end of the study) – will be made to the parents or LARs of the UK reconsented participants by the site personnel to collect any LRTI hospitalizations or related SAEs that might have occurred from D366 to D731 post-dosing/randomization. A memory aid will be provided to the parents or LARs of the UK reconsented participants to record any of these events that may occur during the second year of the study.

During the 12- and 24-month follow-up calls, the site investigator or staff designee will ask to parents/LARs of UK reconsented participants if the participants had experienced any medically attended cough, chest or breathing problems throughout the study period. After the 12-month follow-up phone call (when possible) and the 24-month follow-up phone call, the site investigator or staff designee (including third parties authorized by the site investigators) will access the UK reconsented participants' medical record (general practitioner's or hospital's record) to determine if the medical event meets with the definition of wheeze provided by the Sponsor (see Section 8.1.2.4). If so, the event and related complementary information (including any medications prescribed during wheeze) will be retrospectively collected.

Number of Participants:

A total of 28 860 participants is expected to be randomized. This study is event driven.

For each country, at least 74 events of RSV LRTI hospitalization through the RSV season are needed to ensure the 90% power to conclude the efficacy of nirsevimab in preventing RSV LRTI hospitalization in that country, compared to no intervention, taking the multiplicity adjustment into consideration.

Intervention Groups and Duration:

Eligible participants will be randomized in a 1:1 ratio to receive a single IM injection of 50 mg (if weight < 5 kg) or 100 mg (if weight ≥ 5 kg) of nirsevimab or no RSV preventive intervention on D01. Randomization will be stratified by country and by age group at the time of randomization (ie, age ≤ 3.0 months, age > 3.0 to ≤ 6.0 months, and age > 6.0 months).

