4.1 Overall Design

The design of the study is summarized in Table 4.1.

Table 4.1: Overall design

Type of design	Open-label, multi-center, parallel 2-arm study: nirsevimab compared to no preventive intervention for RSV
Phase	IIIb
Control method	Comparison to no preventive intervention
Study population	Healthy infants born ≥ 29 weeks gestational age (WGA) entering their first RSV season and not eligible for palivizumab (born either in-season or out-of-season)
Level and method of blinding	Open-label
Study intervention assignment method	 Randomization will be stratified by the following: Country Age group at time of randomization (ie, age ≤ 3.0 months, age > 3.0 to ≤ 6.0 months, age > 6.0 months)
Number of participants	28 860 participants
Intervention groups	Eligible participants will be randomized in a 1:1 ratio to receive a single IM injection of 50 mg (if weight < 5 kg) or 100 mg (if weight ≥ 5 kg) of nirsevimab or no RSV preventive intervention on D01
Total duration of study participation	12 months post-dosing/randomization for France, Germany, and UK non-reconsented participants and 24 months post-dosing/randomization for UK reconsented participants
Countries	France, Germany, and the United Kingdom

Use of an Independent Data Monitoring	
Committee, Dose Escalation Committee, or	No
similar review group	

Study Calendar

- Planned date of first participant in: 01 September 2022
- Planned date of last participant in: 28 February 2023
- Planned date of last visit last participant: 28 February 2025

Note: As much as operationally feasible, the date of inclusion of the first participant will be aligned with the beginning of the RSV season. It is thus possible that the first participants are enrolled earlier than 01 September 2022.

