In order to minimize the burden on sites, families and participants, while still answering the objective of this protocol amendment, it was decided to invite in the study extension only the UK participants, who represent 50% of the study population.

Enrollment of Study Participants

A total of 28 860 participants will be enrolled from sites in France, Germany, and the United Kingdom. The study will enroll infants born either out of the RSV season or in the RSV season.

Definition of the RSV season

There is an important variability of RSV seasonality from year to year in each country. The typical RSV season in the Northern Hemisphere (NH) last approximately 5 months and usually starts in October or November. Therefore, the "Out-of-Season" period refers to the approximately 7 months period from March or April to September or October. The actual start date and length of the RSV season will depend on the actual circulation of RSV in the NH in 2022.

Cases of LRTI hospitalization will be collected throughout the study to ensure that all cases occurring during the next RSV season are captured. For the need of this study, the start and end dates of the RSV season will be defined on a country-by-country basis and will be based on country-specific epidemiological surveillance. For the mothers of infants to be born in-season, recruitment will start at 30 weeks gestation in women with an estimated delivery date during the RSV season.

Rationale for the Collection of Safety Data

Immediate AEs

As nirsevimab is not a marketed product, a 30 minutes immediate surveillance period of infants enrolled in the nirsevimab group will be done on the site where immunization was performed.

Non-serious AEs

For a period of 30 days post-dosing/randomization, non-serious AEs will be captured in the eCRF for all study participants. The relation of AEs to interventional product will be determined by the Investigator.

The use of the eDiary by parents and the process for reporting AEs in the eCRF is outlined in Section 8.2.3.

Hospitalizations

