9.2 Sample Size Determination

A total of 28 860 participants are expected to be enrolled of whom approximately 14 430 will receive nirsevimab and 14 430 will receive no intervention. This sample size is driven by the

demonstration of efficacy in preventing RSV LRTI hospitalization in each of 3 countries independently.

Based on the reported incidence rates of RSV LRTI hospitalization in France, Germany, and the UK (2) (51) (52), assuming a 1.1% incidence rate on average in the control group (ie, receiving no intervention), 9620 participants need to be enrolled in each of the 3 countries (which is equivalent to 74 events of RSV LRTI in each country) to ensure the 90% power to detect 60% efficacy in each country with a 2-sided α of 1.66% taking the multiplicity adjustment using Bonferroni approach into consideration.

The sample size of 28 860 participants has at least 99% power to detect 60% efficacy in preventing RSV LRTI hospitalizations in all 3 countries combined assuming an incidence rate of 0.86% in the control group (the lowest reported in the 3 countries) with a 2-sided α of 5%, and approximately 95% power to detect 60% efficacy in preventing very severe RSV LRTI defined in the protocol assuming an incidence rate of 0.4% in the control group (59) with a 2-sided α of 5%. To ensure at least 90% power for very severe RSV LRTI, at least 61 events are needed.

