2.3. Sample Size and Power

A total of 28,860 participants are expected to be enrolled of whom approximately 14,430 will receive nirsevimab and 14,430 will receive no intervention. This sample size is driven by the demonstration of efficacy in preventing RSV LRTI hospitalization through RSV season in each of 3 countries independently.

Based on the reported incidence rates of RSV LRTI hospitalization in France, Germany, and the United Kingdom ^{1,2,3}, assuming a 1.1% incidence rate on average in the no intervention group, 9,620 participants need to be enrolled in each of the 3 countries (which is equivalent to 74 events of RSV LRTI in each country) to ensure the 90% power to detect 60% efficacy (see definition of efficacy of nirsevimab in preventing RSV LRTI hospitalization compared to no intervention in Section 2.4) in each country with a 2-sided α of 1.66% taking the multiplicity adjustment using Bonferroni approach into consideration.

The sample size of 28,860 participants has at least 99% power to detect 60% efficacy in preventing RSV LRTI hospitalizations in all 3 countries combined assuming an incidence rate of 0.86% in the no intervention group (the lowest reported in the 3 countries ^{1,2,3}) with a 2-sided α of 5%, and approximately 95% power to detect 60% efficacy in preventing very severe RSV LRTI defined in the protocol assuming an incidence rate of 0.4% in the no intervention

group with a 2-sided α of 5%. To ensure at least 90% power for very severe RSV LRTI, at least 61 events are needed.

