 - for the participants who had no contact for safety events at all throughout the efficacy follow-up period, the end date for the efficacy follow-up will be date of randomization for participants who are randomized to no intervention, the date of treatment dosing for participants who are randomized to nirsevimab and treated, and the date of randomization for participants who are randomized to nirsevimab but not treated.

The total person-time for the follow-up time of each participant will be calculated as:

Person-months = (the end date - the start date + 1)/30.4375.

NN (days), the total person-time contributed by participants randomized in the nirsevimab, will be the sum of person-months for all the participants in the nirsevimab group. And NC (days), the total person-time contributed by participants randomized in the no intervention group, will be the sum of person-months for all the participants in the no intervention group.

The 2-sided 95% CI for the efficacy will be calculated by an exact method assuming a binomial distribution of the number of RSV LRTI hospitalizations in the nirsevimab group conditional on the total number in both groups (described by Breslow and Day⁷) accounting for the follow-up time post-dosing/randomization.

The superior efficacy of nirsevimab in preventing RSV LRTI hospitalization is concluded if the lower bound of 2-sided 95% CI of the efficacy is $> 0\%$. P-value will also be provided. The primary efficacy analysis of the primary endpoint will be performed with the All Randomized Set.

RSV season is the period of increased RSV infection. For the purpose of efficacy analyses, the start of the RSV season will be defined on a country-by-country basis and will be based on country-specific epidemiological surveillance and the cut-off date (28Feb2023, except for site parent contact and medical call center contact, for which the date of database lock for Primary Analysis will be used) will be used as end dates.

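### The 61-event trigger secures the primary test only: nothing in the plan ensures the event counts behind the stated very severe and per-country powers, and 9,620 infants per country does not fit a 50% UK share

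*Protocol*

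**What the plan says.** On analysis timing, Protocol 9.4.1 states: "The Primary Analysis will be conducted when at least 61 events of RSV LRTI hospitalization in all 3 countries combined are observed". It sets 30 April 2023 as the latest date, and SAP 6.7.8 repeats both. SAP 6.6.1 uses "the cut-off date (28Feb2023, except for site parent contact and medical call center contact" as the end of the RSV season. Protocol 4.1 gives the same day for the end of enrolment: "Planned date of last participant in: 28 February 2023".

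On event counts, Protocol 9.2 states: "To ensure at least 90% power for very severe RSV LRTI, at least 61 events are needed". The synopsis calls the study event driven and adds: "For each country, at least 74 events of RSV LRTI hospitalization through the RSV season are needed to ensure the 90% power". Protocol 9.2 specifies that "9620 participants need to be enrolled in each of the 3 countries", which SAP 2.3 glosses as "which is equivalent to 74 events of RSV LRTI in each country".

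On the country split, Protocol 4.2 explains that the extension invites "only the UK participants, who represent 50% of the study population".

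On testing, Protocol 9.1 places the primary and both key secondary objectives in the Primary Analysis, in fixed order: primary, very severe RSV LRTI, then the three countries with Bonferroni-Holm. Protocol 9.4.1 and 9.5 make later efficacy analyses descriptive or exploratory.

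**The concern.** In the sample size section, 61 is the number of very severe cases needed. In the timing rule, 61 counts all RSV LRTI hospitalizations, of which very severe cases are a subset. The country requirement of 74 does not appear in the timing rule at all. Neither calendar date carries an event minimum, and an infant enrolled shortly before 28 February 2023 adds almost no follow-up.

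The very severe test is the gate to the country tests, and the country tests drove the sample size. There is no later confirmatory analysis. A non-significant very severe or country result would therefore be read against a stated 95% or 90% power that the timing rule does not secure.

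A second question concerns the country power. It rests on one third of the sample in each country, while the current protocol text puts half of it in the UK.

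**Working it through.** **Inputs.** From Protocol 9.2: 28,860 infants, 9,620 per country, 60% efficacy, control incidences of 1.1% (country), 0.86% (overall) and 0.4% (very severe), two-sided alpha of 1.66% per country and 5% otherwise. Randomization is 1:1. Protocol 9.4.2 gives the exact test conditional on total events. Protocol 4.2 gives a season of about 5 months, usually starting in October or November. Section 9.2 gives no time base for the incidences.

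**Method.** With D events and equal person-time, the nirsevimab count is binomial with p = 0.5 under the null and p = 0.4/1.4 = 0.2857 at 60% efficacy. The test succeeds when the lower tail at 0.5 is at most alpha/2.

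**The plan's own figures reproduce.**
- D = 61, alpha 5%: success at 22 or fewer events, power 92.2%.
- D = 74, alpha 1.66%: success at 26 or fewer, power 91.4%.
- Expected per country: 4,810 × 0.011 × 1.4 = 74.1 events. Power averaged over a Poisson count is 89.5%.
- Expected very severe: 14,430 × 0.004 × 1.4 = 80.8 events, averaged power 96.9%.

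The stated powers therefore hold if the full expected counts are in the data.

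**Trigger against requirement.** At exactly 61 hospitalizations the primary test has 92.2% power. Reaching 61 very severe cases would take about 61 × 0.86/0.4 = 131 to 61 × 1.1/0.4 = 168 hospitalizations. Reaching 74 in each country takes at least 3 × 74 = 222.

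**Power at the cut-off, equal country split.** Assume that 1.1% and 0.4% are full-season risks, spread evenly over a 5-month season from 1 October or 1 November. Expected events are then multiplied by the average share of the season that infants spend enrolled by 28 February 2023. For uniform September-February accrual, in months, the share is (1 × 1 + 5 × 0.5)/6 = 0.58 for an October start. For a November start, four of the five season months fall before the cut-off, so it is (2 × 0.8 + 4 × 0.4)/6 = 0.53. Counting days gives the values below (October / November start).

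| Accrual (assumed) | Share | Events per country | Country power | Very severe events | Very severe power |
|---|---|---|---|---|---|
| (a) Uniform Sep-Feb | 0.586 / 0.533 | 43.4 / 39.5 | 63.3 / 57.8% | 47.3 / 43.1 | 82.0 / 77.8% |
| (b) Uniform Sep-Dec | 0.773 / 0.695 | 57.2 / 51.5 | 78.4 / 73.0% | 62.4 / 56.2 | 91.7 / 88.5% |
| (c) All by season start | 1.000 / 0.795 | 74.1 / 58.9 | 89.5 / 79.8% | 80.8 / 64.2 | 96.9 / 92.4% |

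If the rates are in-study incidences, no discount applies and the October figures of row (c) hold. Even at 0.86%, the primary test has 14,430 × 0.0086 × 1.4 = 173.7 expected events, falling to 101.7 / 92.7 under (a), with power 99.1 / 98.5%.

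**Country split.** Half of 28,860 is 14,430, so France and Germany share 14,430 and at least one has at most 7,215. That gives 7,215/2 × 0.011 × 1.4 = 55.6 events with full follow-up, a 1% chance of reaching 74, and 76.9% power at 1.66%. With 25% in each of France and Germany (assumed), simulating the planned Holm procedure gives about 87% for each, or 85% after the very severe gate. Under accrual (a) the same split gives about 52-58% with Holm, before the gate.

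**The case against.** Several counter-arguments carry weight.

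- **61 is a minimum.** All available data up to the cut-off are analysed, and the planned totals are about 222 hospitalizations and 81 very severe cases. A reader might infer that the key secondary tests were expected to run at the trigger count, with about 24% power per country (equal split) and 45-56% for very severe disease. The documents do not support that. Those figures are a lower limit, not the expected state.
- **Protocol 9.2 already states counts.** It requires 9,620 infants in each country and 61 events for 90% very severe power. It would be wrong to say that the equal split is an unstated condition. What is missing is any link from these counts to the timing rule, and a time base for the incidences.
- **The 50% UK share looks realised.** It belongs to the rationale for the extension introduced by the amendment of 19 July 2023, after planned enrolment ended. A reader might infer two contradictory planning assumptions, but the documents do not establish that. They also give no realised total or France/Germany split, so 7,215 and 56 are illustrations at the planned size. Still, both figures stand unreconciled in the current text.
- **Accrual may have been early.** Protocol 4.1 aligns first inclusion with the season, and 4.2 envisages immunizing the cohort at its start. That favours row (c). However, Protocol 10.1.3 also allows recruitment during the season and enrols in-season births as they occur.
- **Holm is the planned test.** Hence 87%, not 77%, is the relevant figure for France and Germany with full follow-up.
- **Efficacy may exceed 60%.** Protocol 2.3.2 cites 78.4% in preterm infants. At that value accrual (a) gives 92-95% per country (equal split, 1.66%) and 98-99% for very severe disease. The population differs, and the stated powers are for 60%.

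**Conclusion.** The point holds for the key secondary tests only. The timing rule, the 30 April 2023 limit and the 28 February 2023 cut-off do not ensure 61 very severe cases or 74 hospitalizations per country. Under the labelled assumptions, equal-split country power at the cut-off lies between about 58% and 90%, and very severe power between about 78% and 97%. The position within each range depends on accrual, season start and the unstated incidence time base. The stated powers are attainable, but not secured.

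A 50% UK share at 28,860 infants would leave at least one other country at about 56 events rather than 74. With 25% in each of France and Germany and full follow-up, the planned Holm procedure gives about 87% there, before the gate.

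A reader might also infer that the trigger is invalid or inflates type I error. It does neither: it is an adequate minimum for the primary endpoint, and the fixed testing order controls alpha.

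**What to change.** Leave the trigger, data and tests of the completed Primary Analysis unchanged.

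1. In Protocol 9.4.1 and SAP 6.7.8, state that 61 hospitalizations is a minimum that supports the primary endpoint only. If the protocol is not amended again, put this in SAP section 7 and the study report.
2. In Protocol 9.2 and SAP 2.3 (or the same alternative places), restate the very severe and country powers as holding only if 61 very severe cases and 74 hospitalizations per country are reached by the cut-off. Name the incidence time base and the accrual and country-split assumptions.
3. Reconcile 9,620 per country with the 50% UK share, say whether that share is planned or realised, and give the France and Germany power under Holm.
4. Report the observed event totals for each key secondary test against 61 and 74. The exact confidence intervals already show the precision.

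The cost is wording and a few event totals. A protocol amendment would need ethics approval under Protocol 10.1.1, which the SAP and report route avoids. The documented key secondary powers become conditional and, for France and Germany, less favourable.
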